##### **6.1.2.1 Placebo Effect**

An analysis of the primary endpoint will be conducted using the data from the BPI Question 3 to evaluate the placebo effect in the overall study population. The proportion of successes at the End of Sham visit (Visit 4) will be compared to the proportion of successes at the End of Trial Stage in order to determine the pain intensity reduction during the sham period compared to 3-weeks of SPR Trial Stage stimulation. The Wilcoxon signed rank test will be used to assess the significance of the median change in BPI3.

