The proportion of subjects achieving success in each stage will be calculated. A 2-point reduction in pain intensity is considered to be the minimum clinically important difference (MCID) on a 0-10 pain numeric rating scale (Farrar et al., 2001). Primary efficacy of the Trial Stage therapy will be determined at the end of the Trial Stage. Primary efficacy of the Implant Stage will be determined at the 12-week post-IPG Stim On follow-up visit. A subject will be considered a Trial Stage Success if he/she achieves at least a 2-point reduction in post-stroke shoulder pain intensity score in the BPI Pain Intensity Question #3 (BPI3) at the end of the Trial Stage (Visit 5) relative to end of the placebo period or baseline (Visit 4 or Visit 1), whichever is lower OR reports a BPI3 score of zero at the end of the Trial Stage.

In addition, the average reduction in pain intensity across all subjects during each stage will be analyzed.

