#### **5.4.1.1 Determination of Placebo Effect During SPR Trial Stage**

For each subject, a within subject analysis will be performed to evaluate if a placebo effect occurred during the sham stimulation period. The BPI3 score collected at the End of the sham period (Visit 4) will be compared to the BPI3 score collected at Baseline (Visit 1).

If

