**$P_0$  = BPI pain score at Baseline**

**$P_1$  = BPI pain score at End of Sham**

Then, a positive placebo effect is present in any subject who has a decrease in their BPI3 score from Baseline to the End of Sham:

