##### **6.1.2.2 SPR Trial Stage Success**

Trial Stage success for each subject is the binary outcome pertaining to success (a 2-point or greater decrease in BPI3 during the Trial Stage or failure (a decrease of less than two points, no change in BPI3, or increase of BPI3 during the Trial Stage). BPI3 at the end of the Trial Stage (Visit 5) will be compared to BPI3 at the End of Sham (Visit 4) for subjects who demonstrate either no placebo or a positive placebo effect. For subjects in whom a negative placebo effect was observed, BPI3 results at Visit 5 will be compared against Baseline (Visit 1).

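### The sham-versus-stimulation comparison of success proportions leaves sham success undefined and scores stimulation against a raised hurdle in subjects who worsened on sham

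*Combined protocol and SAP*

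**What the plan says.** Section 6.1.2.1 sets Visit 4 against the end of the Trial Stage: "The proportion of successes at the End of Sham visit (Visit 4) will be compared to the proportion of successes" at the later visit, "in order to determine the pain intensity reduction during the sham period compared to 3-weeks of SPR Trial Stage stimulation". That is a contrast of two periods. The section adds: "The Wilcoxon signed rank test will be used to assess the significance of the median change in BPI3". It does not say which change is meant, and it names no test for the two proportions.

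For the sham period, section 5.4.1.1 gives the reference: "The BPI3 score collected at the End of the sham period (Visit 4) will be compared to the BPI3 score collected at Baseline (Visit 1"). The only sham-period response that the plan defines has no 2-point threshold: "a positive placebo effect is present in any subject who has a decrease in their BPI3 score from Baseline to the End of Sham". No section defines success at Visit 4.

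For Visit 5, section 4.4.1.1 defines Trial Stage Success as a fall of at least 2 points "relative to end of the placebo period or baseline (Visit 4 or Visit 1), whichever is lower", or a score of zero. Section 5.4.1.2, Table 9 and section 6.1.2.2 apply the same reference in two branches: End of Sham for subjects who improved or did not change on sham, and Baseline for those who worsened. Section 5.4.1.2 explains the Baseline branch as a way to keep placebo response out of the credited relief.

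**The concern.** Using the lower of two scores is a reasonable hurdle for the primary endpoint. In section 6.1.2.1 it acts on one side only. Sham must be scored from Visit 1. Stimulation is scored from its own starting point, Visit 4, unless the subject worsened on sham, and then from the lower Visit 1 score. No matching penalty applies to sham.

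Two mirror-image subjects show this. Scores of 6, 4, 6 at Visits 1, 4 and 5 give a sham success (6 − 4 = 2). Scores of 6, 8, 6 contain the same 2-point fall during stimulation (8 − 6 = 2), but the plan's rule gives 6 − 6 = 0, a failure.

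The sham period was included to gauge placebo response, and the pilot is meant to inform a pivotal study. If equal responses can read as sham doing better, or a real difference is diluted, that reading is misleading.

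**Working it through.** The plan gives no figure to reproduce for this comparison. The sample-size section and the success-rate hypotheses are blacked out, which is not a fault in the plan.

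**Rules.** P0, P1 and P2 are the BPI3 scores at Visits 1, 4 and 5.
- Sham success: P0 − P1 ≥ 2. The threshold is assumed, because the plan gives none.
- Stimulation success under the plan: min(P0, P1) − P2 ≥ 2, or P2 = 0.
- Stimulation response from its own start: P1 − P2 ≥ 2.

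Entry requires P0 ≥ 4, so the zero route changes a result only when P1 is 0 or 1. For anyone else, P2 = 0 is already a fall of at least 2.

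**Inputs.** From the documents: integer scores 0–10, entry at 4 or more, up to 45 Trial Stage subjects. Assumed: true pain mean 7, SD 1.5; independent visit error SD 1.5 (also 1.0); exact two-sided McNemar test at 0.05. Rates are simulated from 400,000 subjects per setting, and rejection rates from 4,000 trials of 45.

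**Results at error SD 1.5.**

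| True fall, sham / stimulation | Sham success | Stimulation, plan's rule | Stimulation, own start |
|---|---|---|---|
| 0 / 0 | 23.7% | 11.8% | 22.6% |
| 1 / 1 | 41.2% | 32.9% | 40.3% |
| 2 / 2 | 60.5% | 57.9% | – |

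- With no effect, McNemar favours sham in 21% of trials under the plan's rule and in 2% when each period is scored from its own start.
- With 1-point falls it favours sham in about 7.5% of trials under the plan's rule; with 2-point falls, in about 2.5%.
- With falls of 1 (sham) and 2.5 (stimulation), power to show stimulation better is 37% under the plan's rule and about 50% from each period's own start.

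**Results at error SD 1.0.** With no effect, 14.5% versus 5.9% (own start 14.1%). With 2-point falls, 63.7% versus 63.5%. Power for falls of 1 and 2.5 is 83% versus 87%.

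**Where the gap comes from.** With no effect and error SD 1.5, about 37% of subjects score worse at Visit 4 by chance. For everyone else the two stimulation scorings agree, apart from the zero route. The loss of 22.6 − 11.8 = 10.8 points therefore falls on that 37%, and costs them about 10.8 / 0.37 = 29 percentage points of response.

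**Sensitivity to the model.** Suppose instead that each period's fall is an independent draw from one distribution (mean 0, 1 or 2; SD 1.5 to 2.5; mean baseline about 7.3). The gap is then 0 to 6 points, and McNemar favours sham in about 1.5% to 6% of trials. The direction is the same and the size smaller.

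**The case against.** Four points on the other side have weight.

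1. The 2-point sham threshold is inferred. The firmer defect is an undefined term. That stands. If success at Visit 4 were read as any decrease, the sham rate could only rise and the mismatch would grow.

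2. A reader might infer that equal response always looks like sham winning. The documents do not support that. For subjects who do not worsen on sham, sections 5.4.1.2 and 6.1.2.2 already score each period from its own start. Enumerating every score path with an equal fall in both periods gives no case that counts for sham only. The bias enters only through subjects who score worse after sham, and at 2-point falls it nearly vanishes.

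3. A reader might take this for the plan's only contrast of stimulation with sham. It is not. Section 6.1.2.1 also names a Wilcoxon test, section 6.1.2 compares Visit 5 data with End of Sham or Baseline, and Trial Stage Success is itself built on that comparison.

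4. Per-period scoring is not neutral under every meaning of equal response. If stimulation merely holds a sham-period gain, it still shows sham ahead: 41% versus 24% after a 1-point sham fall (sham favoured in 26% of trials), and 60% versus 24% after a 2-point fall (82%). Scoring both periods from Baseline removes that gap, but then favours stimulation when the falls are equal (37.0% versus 59.7% in the independent-draw model with mean 1, SD 1.5), because the sham gain is carried forward. No single reference serves both meanings. Section 6.1.2.1 states a per-period aim, which settles the choice, but the limitation should be written down.

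**Conclusion.** The point holds in a limited form. Section 6.1.2.1 does not define success at Visit 4. Applying the plan's only Visit 5 success definition there handicaps stimulation in subjects who worsened on sham, against the section's own per-period aim.

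On the assumptions above, the handicap is about 12 percentage points with no effect, 8 with 1-point falls and 2 to 3 with 2-point falls. The power loss is about 13 points at error SD 1.5 and 4 at error SD 1.0. All means and SDs, the sham threshold and the McNemar test are assumptions; the documents give none of them.

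It would be wrong to conclude that the primary efficacy result is biased. Section 6.1.2.4 tests the success rate against a fixed value, not against sham, and the lower-of-two rule is a deliberate, conservative choice there. The effect is confined to the placebo-effect comparison of proportions, and it runs against the device. The change is still worth making, because it costs little and this comparison sets the sham period directly against stimulation.

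**What to change.** For section 6.1.2.1 only:

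- State that the quantity of interest is the reduction within each 3-week period.
- Define sham response as Visit 1 minus Visit 4 of at least 2, and stimulation response as Visit 4 minus Visit 5 of at least 2, with no zero-score route.
- Compare the paired proportions with an exact McNemar test.
- State that the Wilcoxon signed rank test compares the two within-subject changes.
- Note that this contrast scores maintenance of a sham-period gain as no further response.

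Keep the lower-of-two rule for Trial Stage Success. The cost is SAP wording, with no new data. Two Visit 5 proportions will then be reported, so each needs a distinct label, for example Trial Stage Success and stimulation-period response.

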Subjects will use the Smartpatch System for 6-weeks during the Trial Stage. To evaluate the placebo effect, the first 3-weeks of the SPR Trial Stage consist of a sham period in which the SPR Trial Stage device (i.e., the Smartpatch System) is placed, but stimulation is not delivered. Subjects are told that stimulation during lead placement may feel different than stimulation therapy. [REDACTED]

[REDACTED] Subjects will be blinded to the fact that stimulation is not being delivered. Following the sham period, stimulation will be delivered, and subjects will receive stimulation for a total of 6 hours each day for 3 weeks. Subjects will be queried for pain intensity on a weekly basis during the SPR Trial Stage using the BPI Short Form Question #3 (BPI3), and subjects will be instructed to focus on their shoulder pain when answering the BPI. Pain intensity at the end of the sham period will be compared to baseline pain intensity score to evaluate the placebo effect. At the conclusion of the SPR Trial Stage, subjects achieving at least a 2-point reduction on the BPI3 will receive monthly follow-up calls for up to six months in order to determine eligibility to advance to the SPR Implant Stage. During the Implant Stage, subjects will receive the fully implantable SPR Implant Stage system and be followed for three years.

All primary and secondary endpoints will be assessed at baseline and again at the completion of the sham period and the SPR Trial Stage. In addition, primary endpoints will be evaluated at all phone calls during the Trials Stage follow-up period and at all follow-up intervals during the SPR Implant Stage (3-weeks, 6-weeks, 12-weeks, 6-months, 9-months, and 12-months post IPG Stim ON). In addition, long-term follow-up will be conducted on an annual basis at 24-Months and 36-Months IPG Stim On.

Primary efficacy of the Trial Stage therapy will be determined at the end of the Trial Stage. Primary efficacy of the Implant Stage will be determined at the 12-week post-IPG Stim On follow-up visit. A subject will be considered a Trial Stage Success if he/she achieves at least a 2-point reduction in post-stroke shoulder pain intensity score in the BPI Pain Intensity Question #3 (BPI3) at the end of the Trial Stage (Visit 5) relative to end of the placebo period or baseline (Visit 4 or Visit 1), whichever is lower OR reports a BPI3 score of zero at the end of the Trial Stage.

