#### 4.4 Study Endpoints

##### 4.4.1 Primary Endpoints

###### 4.4.1.1 Reduction in pain intensity (Brief Pain Inventory)

The primary endpoint of the study is reduction in pain intensity over the past week as measured using the 11-point numerical rating scale of the Brief Pain Inventory (BPI3). The BPI is a widely used and validated assessment designed to measure pain intensity and the interference of pain on daily activities and moods (Cleeland and Ryan, 1994).

The BPI is recommended by the Initiative on Methods, Measurement, and Pain Assessment in Clinical Trials (IMMPACT) panel and has demonstrated validity and reliability across many cultures and languages (Cleeland and Ryan, 1994; Tan et al., 2004; Dworkin et al., 2005). The IMMPACT panel was assembled to develop consensus recommendations to improve and standardize the design and conduct of clinical trials involving treatments for pain. Invited participants included academic centers, regulatory agencies, the National Institutes of Health, the US Veterans Administration, and industry representatives. In addition, the BPI has been used in many chronic pain studies, including those for post-stroke shoulder pain, which demonstrated a significant reduction in pain intensity as compared to a standard of care control (Chae et al., 2005; Yu et al., 2004).

All subjects will be evaluated for a reduction in their worst pain intensity in the previous week (BPI3) at several key study visits: (1) at the completion of the 3-week sham period (Visit 4) to evaluate the placebo effect; (2) at the completion of the 3-week SPR Trial Stage stimulation period (Visit 5) to determine if the subject has met the criteria to be a Trial Stage Success; (3) during the Trial Stage follow-up period to assess for Implant Stage eligibility, and (4) at 3-weeks (Visit 8), 6-weeks (Visit 9), 12-weeks (Visit 10), 6-months (Visit 11), 9-months (Visit 12), 12-months (Visit 13), 24-months (Visit 14), and 36 months (Visit 15) following

the initiation of IPG Stimulation to determine efficacy of the implantable system. The BPI will be administered with stimulation turned off (for at least one hour prior to the study visit) and subjects will be instructed to focus on their shoulder pain when responding to the questions presented in the BPI.

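### Section 6.1.2.1 sets out to compare sham with stimulation, but its one named test is on an unspecified BPI3 change, Visit 4 success is undefined, and no paired test of the two proportions is given

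*Combined protocol and SAP*

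**What the plan says.** Section 6.1.2.1 (Placebo Effect) states: "The proportion of successes at the End of Sham visit (Visit 4) will be compared to the proportion of successes" at the end of the Trial Stage. The stated purpose is to set the fall in pain over sham against the fall over three weeks of stimulation. The next and last sentence names the only test: "The Wilcoxon signed rank test will be used to assess the significance of the median change in BPI3". Nothing in this section is blacked out, so what is absent is absent from the plan.

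Related text:

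- Section 6.1.2.2 defines the Trial Stage outcome as "success (a 2-point or greater decrease in BPI3 during the Trial Stage or failure". Section 4.1 measures it "relative to end of the placebo period or baseline (Visit 4 or Visit 1), whichever is lower", and also counts a BPI3 of zero at Visit 5 as success. No section defines success at Visit 4.
- Section 4.1 fixes the order: "the first 3-weeks of the SPR Trial Stage consist of a sham period in which the SPR Trial Stage device" is in place without stimulation. Every subject has sham first, and there is no concurrent control.
- Section 6.1.2.4 tests the success rate against a fixed, redacted rate, not against the sham rate.

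**The concern.** The sham period is there to show how much of the improvement occurs without stimulation. That calls for a within-subject comparison of two periods. The plan leaves three things open: which visits form the tested change, what counts as success at Visit 4, and how two binary outcomes in the same subjects are to be compared.

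Section 6.1.2 says that Visit 5 data will be compared with Visit 4 data, so an analyst could reasonably run the Wilcoxon test on Visit 4 to Visit 5. The title of 6.1.2.1 and the text of 5.4.1.1 point instead to Visit 1 to Visit 4. The first asks whether pain fell during stimulation, the second whether it fell during sham. Neither asks whether it fell more during stimulation. At stake is a significant result being reported as stimulation beating sham when pain was simply still falling, in a pilot meant to inform a pivotal study (Section 1.5).

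**Working it through.** **Inputs from the plan.** P0, P1 and P2 are BPI3 at Visits 1, 4 and 5 (5.4.1.2). BPI3 is an 11-point scale (4.4.1.1). Entry requires P0 of 4 or more (4.2.1). Up to 45 subjects enter the Trial Stage (5.4). The power inputs are redacted and no sample size is visible for sham against stimulation, so there is no figure of the plan to reproduce.

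**Assumed.** Two-sided 5% level, true mean pain 6.5, between-subject SD 1.8, visit-to-visit error SD 0.7 to 1.5, and the size of any drift. None of these is in the documents.

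**Step 1: what each change tests.**

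- P0-P1: change during sham.
- P1-P2: change during stimulation.
- D = (P1-P2)-(P0-P1) = 2·P1-P0-P2: stimulation minus sham.

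A subject scoring 7, 6, 5 has P1-P2 = 1, but D = 12-7-5 = 0. Only D is aimed at the stated purpose.

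**Step 2: the named test does not answer the proportion question.** Suppose all 45 subjects fall by exactly 1 point. Each tied rank is 23, so the rank sum is 45×23 = 1035. The null mean is 45×46/4 = 517.5. The variance is 45×46×91/24 - (45³-45)/48 = 7848.75-1897.5 = 5951.25, SD 77.14. Then z = 517.5/77.14 = 6.71 and p is about 2×10⁻¹¹. Nobody has a 2-point success, barring a score of zero.

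**Step 3: effect of drift.** Simulated trials of 45 (600 per row), integer scores, no stimulation effect; percentage significant in favour of stimulation:

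| Decline in sham / stimulation period | Error SD | Wilcoxon, Visit 4 to 5 | Wilcoxon on D |
|---|---|---|---|
| 0.7 / 0.7 | 0.7 | 98.5 | 1.0 |
| 0.7 / 0.7 | 1.0 | 86.8 | 1.7 |
| 0.7 / 0.7 | 1.5 | 52.3 | 2.0 |
| 1 / 1 | 0.7 | 100 | 1.7 |
| 1 / 1 | 1.0 | 100 | 1.5 |
| 1 / 1 | 1.5 | 85.3 | 1.0 |
| 1 / 0 | 0.7 to 1.5 | 2.0 to 2.2 | 0 |

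With equal declines of 0.5 to 1.0 point and error SD 0.7 to 1.2, the Visit 4 to 5 test favours stimulation in about 38 to 100% of trials and the test on D in 1 to 2%. With the decline confined to sham, the Visit 4 to 5 figure is about 3%.

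**Step 4: the two success definitions must match.** If Visit 4 success is P0-P1 of 2 or more while Visit 5 success uses the lower of P0 and P1, the periods are not treated alike. With no effect in either period, sham success is 11 to 21% and stimulation success 5 to 11% (error SD 0.7 to 1.2), and McNemar is significant in favour of sham in 8 to 17% of trials. In one set-up with stimulation adding 2 points over sham, McNemar detected it in 59 to 79% of trials with the lower-of-two reference and in 88 to 90% with matching definitions.

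**Step 5: power of exact McNemar at 45, independent pairs** (strongest negative association in brackets). The rates are assumed, except that 31% and 84% are the sling and stimulation rates of the earlier randomized trial in Section 2.2.3.

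| Sham | Stimulation | Power |
|---|---|---|
| 20% | 40% | 45% (33%) |
| 20% | 50% | 80% (62%) |
| 30% | 50% | 40% (27%) |
| 31% | 60% | 72% (48%) |
| 31% | 84% | 99.9% (98%) |

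**The case against.** **The text allows a sound reading.** Read as Visit 1 to 4, the Wilcoxon test is a correct test of change during sham. Read with the sentence before it, it could mean a comparison of the two reductions, which is the contrast proposed here. This stands in part: the provable fault is that the contrast is not stated. A reader might infer that the plan cannot show that stimulation beat sham. The documents do not support that, because BPI3 is collected at Visits 1, 4 and 5 and the right contrast can be computed from it.

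**The drift is assumed.** Nothing in the plan gives a decline continuing into the second period, and these subjects have chronic pain. If improvement levels off during sham, the Visit 4 to 5 test is not misled. This stands and limits the size of the claim.

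**The placebo label.** Section 5.4.1.1 says "a positive placebo effect is present in any subject who has a decrease in their BPI3 score from Baseline to the End of Sham", so a 1-point fall counts, although the plan's minimum important difference is 2 points (4.4.1.1). A reader might infer that this distorts the comparison of success. It does not. The label only selects the reference visit: in all 7×11 = 77 combinations of P0 (4 to 10) and P1 (0 to 10), the reference is the lower of the two, and success still needs 2 points or a score of zero. It is true that 32 to 43% of subjects would carry the label with no true change, but in that scenario every label is noise by construction, and 6.1.2.1 draws no inference from the label.

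**The analysis is supporting.** Study success is judged in 6.1.2.4, in a non-randomized pilot. That lowers the weight of the point. It does not remove it, since no other visible analysis tests sham against stimulation.

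**Conclusion.** The point holds as a gap in specification. The tested change, Visit 4 success and the paired test are all missing from 6.1.2.1, and a test of change in one period would not meet the section's own purpose. How misleading that could be depends on drift: about 38 to 100% of trials favouring stimulation under equal declines of 0.5 to 1.0 point, against about 3% if the decline stops with sham. These figures rest on assumed pain levels, error SDs and a two-sided 5% level. Because sham always comes first, no within-subject test fully separates stimulation from time. The contrast D removes a drift that is equal in both periods, and no more than that. The change should be made, but it does not touch the primary endpoint.

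**What to change.** In 6.1.2.1:

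1. Apply the Wilcoxon signed rank test to (P1-P2)-(P0-P1), with an estimate and 95% confidence interval.
2. Define period success alike, as P0-P1 of 2 or more for sham and P1-P2 of 2 or more for stimulation. Compare the two by exact McNemar, with the paired difference and 95% confidence interval. Keep the lower-of-two-visits rule for Trial Stage Success in the primary endpoint only.
3. Report P0-P1 with a confidence interval, described as placebo plus regression to the mean, and state the limit set by the fixed order.

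The cost is wording only; no new data are needed. These tests are less likely to be significant than a test of change alone. With a 1-point fall during sham and 2 points during stimulation, the Wilcoxon test on D detects the difference in 92%, 67% and 34% of simulated trials (error SD 0.7, 1.0, 1.5). McNemar power is moderate for a 20-point difference in success (40 to 45% with independent pairs). Two features work slightly against stimulation and should be noted: regression to the mean after entry at BPI3 of 4 or more falls in the sham period, and a subject at 0 or 1 after sham has no room for a further 2-point fall.
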